7.5.1.4 Handling of Biological Specimens by the Analytical Unit

Biological specimens will be handled and processed as described in the appropriate analytical Method description.

7.5.1.5 Biological Specimens Disposition

As agreed with the Sponsor or 30 calendar days following the final report, samples will be removed from the ultra-freezer and will be stored in a transient warehouse for infectious biological hazard residues until they are collected for their final disposition by an authorized designated company.

7.5.1.6 Ultra-frozen Samples Labeling

Cryotubes will be identified with labels according to the standard operating procedure, code: PPD [REDACTED], early organization for the conduct of an interchangeability and biocomparability study. Each cryotube will state the study number, subject's number, period and number of samples specified in the protocol. Labels will be digitally designed and printed using thermal printer. Label and printing type will ensure that that printing and adhesion resist several freezing and thaw cycles.

7.5.2 Calculation of Pharmacokinetics Variables

The following non-compartmental PK parameters will be calculated from the individual plasma L PZQ and rac-PZQ concentration-time data obtained on Days 1,8 and 15, respectively, using commercial software Phoenix®/WinNonlin® (Version 6.3 or higher).

Table 7 Pharmacokinetic Parameters Derived from L PZQ and rac-PZQ Concentrations

| | |
|-----------|---|
| C_{max} | Maximum observed drug concentration. |
| t_{max} | Time of the maximum drug concentration. |

| | |
|------------------|--|
| t_{lag} | Time prior to the first measurable (non-zero) concentration; calculated as last time point at which the concentration is <LLOQ before the occurrence of the first quantifiable concentration |
| λ_z | Terminal rate constant. |
| $t_{1/2}$ | Terminal elimination half-life. |
| AUC_{0-t} | Area under the drug concentration-time curve from time zero to the time last measurable concentration. |
| $AUC_{0-\infty}$ | Area under the drug concentration-time curve from time zero extrapolated to infinity. |
| $\%AUC_{extra}$ | Percentage of $AUC_{0-\infty}$ obtained by extrapolation |
| $CL_{/f}$ | Apparent clearance |
| $V_{Z/f}$ | Apparent volume of distribution during terminal phase |

The bioanalytical assessment will be outsourced to a third party vendor under the responsibility of Merck. PK parameter estimation and generation of PK TLFs will be outsourced to a third party vendor under the responsibility of Merck. Statistical analysis of Praziquantel will be conducted by the **PPD** [REDACTED], according to their standard operating procedures and in accordance with the NOM-177-SSA1-2013 (28).

CCI [REDACTED]

[REDACTED]

Substance Code
Protocol Number

Praziquantel
MS 200585-0002

Short title Praziquantel Bioequivalence Study

CCI

8 Statistics

8.1 Sample Size

Information on Praziquantel currently available to the WHO PQP Group indicated that the intrasubject variability for Praziquantel is around 50-60% for C_{max} and 35% for AUC, placing this compound in the highly variable drug class. The data from the Merck Serono phase I study performed recently, where Cisticid was used as comparator and different doses of PZQ ODT formulations were examined, confirmed this information and indicated for L-PZQ a CV% of 34.5 for AUC in the overall population and of 39.5% in non-whites, and a CV% for C_{max} of 52%.

The sample size calculation was performed using the R-functions `sampleN.RSABE` and `sampleN.TOST` of the package `PowerTOST`, which takes advantage of the reference-scaled approach suggested by the EMA.

Points to consider:

- For this clinical study comparison, the reference scaled approach is only applicable for C_{max} . For AUC conventional BE limits apply [0.80 – 1.25].
- In general, the reference scaled approach is applicable for $CV \leq 50\%$: For $CVs > 50\%$ fixed BE margins need to be used [0.70 – 1.43].
- Regulatory constant applied for reference scaled approach (EMA): 0.76

The following assumptions were made:

- Assumed true mean Test/Reference ratio for primary PK: 0.95
- C_{max} Coefficient of variation (Reference): 45 - 55%
- C_{max} Coefficient of variation (Test): 45 - 55%
- AUC Coefficient of variation (Reference): 39.5%
- AUC Coefficient of variation (Test): 39.5%
- One-side alpha: 0.05 (corresponds to 90% confidence level)
- Power: 80%
- Drop-out (DO) rate: 20% (agreed with CRO)

For this comparison the conventional BE margins [0.80 – 1.25] need to be applied for AUC. Therefore the rather high CV for AUC of L-PZQ determines the sample size for this trial. CCI

Together with the assumptions above, 48 evaluable subjects will provide 80% power to demonstrate BE. Taking a drop-out rate of 20% into account, 60 subjects should be randomized in this BE trial.

8.2 Randomization

Valid statistical inferences are generally derived by assuming that errors in the observations are distributed independently, in random variables. Randomization generally ensures validity of this hypothesis. Full randomization of subjects to the treatment's sequence will be made according to the design sequences based on the internal procedures from the PPD [REDACTED] compliant with the PPD [REDACTED] (28) using the PPD [REDACTED].

A total of 60 subjects are to be enrolled in the trial and randomized to one of 3 treatment sequences, such that 20 subjects are assigned to each treatment sequence.

8.3 Endpoints

Statistical analysis for determining bioequivalence will be calculated using the computer program package SAS® System PPD [REDACTED].

8.3.1 Primary Endpoints

The primary endpoints are the PK parameters AUC_{0-t} and C_{max} for L-PZQ.

8.3.2 Secondary Endpoints

- Additional pharmacokinetic parameters will be estimated: t_{max} , t_{lag} , $AUC_{0-\infty}$, AUC_{extra} , $t_{1/2}$, λZ , CL/f and Vz/f of L-PZQ and t_{max} , t_{lag} , AUC_{0-t} , $AUC_{0-\infty}$, AUC_{extra} , C_{max} , $t_{1/2}$, λZ , CL/f and Vz/f parameters of rac-PZQ.
- To assess safety and tolerability of 1200 mg of the Cisticid tablets administered in fed condition. Safety will be assessed by AEs, standard laboratory parameters hematology, biochemistry, urinalysis, and coagulation), vital signs (body temperature, systolic blood pressure, diastolic blood pressure, and pulse rate) and 12-lead electrocardiogram (ECG) Analysis Sets

Table 8 Analysis Sets

For purposes of analysis, the following analysis sets are defined:

| Population | Description |
|-----------------|--|
| Enrolled | All participants who sign informed consent |
| Safety | The Safety Analysis Set will include all subjects who receive at least one dose of trial treatment. Subjects will be analyzed according to the actual treatment they receive. |
| Pharmacokinetic | All subjects that received all administrations of treatment and have PK parameters for AUC_{0-t} and C_{max} in all periods and without any relevant protocol violations and factors likely to affect the comparability of PK results. |

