5.1 Overall Trial Design and Plan

The purpose of the current relative bioavailability trial is to assess the bioequivalence (BE) of the the new 600 mg Cisticid tablet (Test) versus Biltricide (Reference) in healthy male volunteers under fed conditions.

This is a phase I, crossover, open-label, single dose, randomized, three period trial where subjects will be randomized to one of three sequences: T-R-R, R-T-R and R-R-T where T is test product and R is Reference product, with a washout period of at least 1 week in between.

The study will investigate the BE of the new 600 mg Cisticid tablet versus the comparator 600 mg tablet of Biltricide at a dose of 1200 mg (primary endpoints AUC_{0-t} and C_{max} of L-PZQ), administered in fed condition in 60 healthy male volunteers. Finally safety and tolerability will be also investigated.

In each treatment period subjects are institutionalized the evening before dosing until 24 hours after dosing with a washout period of 7 days. Total duration of the study for a subject is up to 7 weeks, including a Screening period of maximal 28 days, and 3 weeks dosing period including washout, and safety follow-up (EoT visit) at 7 days after third dose (period).

The subjects will be randomized to one of the 3 treatment sequences (see [Table 2](#) below).

Table 2 Treatment Sequences of the Study.

| Sequence | Period 1 | | Period 2 | | Period 3 | |
|----------|-----------|-----------------|-----------|-----------------|-----------|-------------------------------|
| 1 | Test | Wash-out 7 days | Reference | Wash-out 7 days | Reference | Wash-out 7 days and EOT visit |
| 2 | Reference | | Test | | Reference | |
| 3 | Reference | | Reference | | Test | |

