Subjects are free to discontinue the trial at any time without giving their reasons.

A subject must be withdrawn in the event of any of the following:

- Withdrawal of the subject's consent.
- Non-compliance that jeopardizes subject safety or the validity of the trial data, including lost to follow-up.
- Participation in any other trial during the duration of this trial.
- Use of a non-permitted concomitant drug as defined in section 6.5.2 Prohibited medicines, where the predefined consequence is withdrawal from treatment with investigational medicinal product (IMP).

- Occurrence of AEs, if discontinuation from the trial due to drug effects is desired or considered necessary by the Investigator and/or the subject (if applicable), e.g. severe unacceptable gastrointestinal side effects or inter-current illness.
- Signs of liver injury, as defined by:
 - Alanine aminotransferase (ALT) or aspartate aminotransferase (AST) > 5 x upper limit of normal (ULN).
 - ALT or AST > 3 x ULN and total bilirubin > 2 x ULN or international normalized ratio (INR) > 1.5 x ULN.
 - ALT or AST > 3 x ULN with clinical symptoms of hepatitis such as fatigue, nausea, vomiting, right upper quadrant pain or tenderness, fever, rash and/or eosinophilia (> 5%).
- Vomiting within the first 6 hours after study drug administration, as vomiting interferes with the PK assessments in this study.
- Not consuming the whole breakfast before/during drug administration

Subjects may withdraw consent to participation in the clinical trial at any time without penalty and for any reason without prejudice to future medical care. Withdrawal of consent will be considered withdrawal from the trial.

If a subject failed to attend scheduled trial assessments, the Investigator must determine the reasons and the circumstances as completely and accurately as possible. If a subject is withdrawn, or chooses to withdraw, from the clinical study for any reason, the Investigator must make every possible effort to perform the evaluations described for the EOT visit (see Appendix 2). If there is a medical reason for withdrawal, the subject will remain under the supervision of the Investigator until satisfactory health has returned. In all cases, the reason(s) for withdrawal must be recorded in the case report form (CRF).

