8.4.2 Analysis of Primary Endpoints

The analysis of the primary endpoints AUC_{0-t} and C_{max} of L-PZQ will be performed using the PK population. For the demonstration of bioequivalence different approaches will be applied for AUC_{0-t} and C_{max} . For AUC_{0-t} the standard approach will be followed, i.e. the point estimate and the 90% CI of the Test/Reference geometric mean ratio must fall within [0.80, 1.25]. AUC_{0-t} of L-PZQ will be log-transformed and analyzed using a generalized linear model as given by the SAS code below:

```
PROC GLM DATA=PK;
```

```
CLASS SEQ SUBJ PER TRT;
```

```
MODEL LNPARAM = SEQ PER TRT SUBJ(TRT) / DDFM=SATTERTH;
```

LSMEANS TRT / ADJUST=T PDIFF CL ALPHA=0.10.

TEST H=SEQ E=SUBJ(TRT);

RUN;

QUIT;

The treatment difference TEST – REFERENCE will be estimated, and the 90% CIs for the difference in LS-means will be calculated. The difference and 90% CIs will be back-transformed to the original scale. If the 90% CI for the ratio (test/reference) lies entirely within the interval [80.00 – 125.00], then the BE criterion is fulfilled for AUC_{0-t} .

For the analysis of C_{max} , a reference-scaled bioequivalence approach will be applied as follows:

Point estimate and 90% confidence interval will be computed as described above for AUC. If $CV_{WR} \leq 30\%$ for C_{max} (i.e. the within-subject CV for the reference drug is $\leq 30\%$), then the common acceptance range for bioequivalence will apply. For $30\% < CV_{WR} \leq 50\%$ the acceptance interval will be widened according to $[U, L] = \exp [\pm k \cdot sWR]$, where U is the upper limit of the acceptance range, L is the lower limit of the acceptance range, k is the regulatory constant set to 0.760 and sWR is the intrasubject standard deviation of the log-transformed values of C_{max} of the reference product. sWR will be calculated using the data under reference treatment only. For all values of CV_{WR} greater than 50% the acceptance range is fixed to [69.84 – 143.19].

The geometric mean ratio for C_{max} should always lie within [80.00 – 125.00].

- a. Descriptive statistics and boxplots will be provided by treatment.

CCI

PROC GLM DATA=PK;

CLASS SEQ SUBJ PER TRT GROUP;

MODEL LNPARAM = SEQ PER TRT GROUP GROUP*TRT SUBJ(TRT) / DDFM=SATTERTH;

LSMEANS TRT / ADJUST=T PDIFF CL ALPHA=0.10.

TEST H=SEQ E=SUBJ(TRT);

RUN;

QUIT;

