8.6 Deviation and Exclusion to the Statistical Analysis

All deviations should be justified with statistical or scientific data and any change to the original statistical plan should be documented, in the study master file and in the pharmacokinetics statistical report as well as in the final study report. Subjects' data will not be replaced. Any missing data will be considered as non-existent data. Likewise, data cannot be removed from the statistical analysis, except in the following events.

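### Table 8 admits only three-period completers to the PK set, so usable Test-Reference and Reference-Reference pairs are discarded; planned power is not missed, but some extra precision is given up

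*Protocol*

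**What the plan says.** The design is a partial replicate: "subjects will be randomized to one of three sequences: T-R-R, R-T-R and R-R-T", "such that 20 subjects are assigned to each treatment sequence" (Protocol 5.1 and 8.2).

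Table 8, printed under Protocol 8.3.2, restricts the PK set to "All subjects that received all administrations of treatment and have PK parameters for" AUC0-t and Cmax in all periods, without relevant violations. Protocol 8.4.2 says the analysis of both primary endpoints "will be performed using the PK population". SAP 10.1 has analysis sets in its title but does not redefine this one.

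Other text bears on the same question:

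- Protocol 8.6 says "data cannot be removed from the statistical analysis, except in the following events". The events listed are a pre-dose concentration above 5% of Cmax, and vomiting or diarrhoea. SAP 10.1 adds very low concentrations. A missing period is on neither list.
- Protocol 8.4.1 has data evaluated as observed, without imputation (apart from AE dates and times).
- SAP 10.1 frames evaluability in a crossover by Test and Reference data, not by three periods. Its sentence is garbled: read literally it excludes subjects who do have both.
- SAP 8.1 specifies a mixed model with random subject within sequence. The code printed in Protocol 8.4.2 and SAP 8 nests SUBJ in TRT instead.
- Protocol 5.5.2 requires withdrawal for several post-dose events, for example "Vomiting within the first 6 hours after study drug administration, as vomiting interferes with the PK assessments in this study". Protocol 5.5 does not replace withdrawn subjects.

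**The concern.** The Test/Reference ratio needs one Test and one Reference observation per subject. The second Reference is there for sWR in the Cmax scaling (Protocol 5.2). A TRR or RTR subject who finishes Periods 1 and 2 and is lost in Period 3 has a full within-subject comparison, yet Table 8 removes him. An RRT subject lost at the same point has no Test value but does have both Reference values that sWR uses, and Table 8 removes those too. The event that removes him says nothing against his earlier periods.

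At stake are the precision of the AUC0-t comparison, which determines the sample size, and the clarity of the primary dataset. Table 8, Protocol 8.6 and SAP 10.1 do not describe inclusion in the same terms, so two analysts could build different sets.

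**Working it through.** **Inputs.** From Protocol 8.1: "Assumed true mean Test/Reference ratio for primary PK: 0.95"; "One-side alpha: 0.05 (corresponds to 90% confidence level"); AUC within-subject CV 39.5% for both products; limits 0.80 to 1.25; 48 evaluable, 60 randomised. Drop-out timing is not in the documents and is assumed below.

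**Step 1: the plan's own figure.**
- s = sqrt(ln(1 + 0.395²)) = 0.381.
- A completer's contrast, Test minus the mean of two References, has variance s²(1 + 1/2) = 1.5s². With 48 completers the standard error is 0.381 × sqrt(1.5/48) = 0.0673, on 2 × 48 − 3 = 93 degrees of freedom.
- Exact two-one-sided-tests power at a ratio of 0.95 is 80.5% (79.9% with the more cautious 45 degrees of freedom). The smallest balanced n reaching 80% is 48, and 48/(1 − 0.20) = 60. The plan reproduces.

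**Step 2: what a pair is worth.** One Test and one Reference give variance 2s². Information in units of 1/s² is 1/2, against 1/1.5 = 2/3 for a completer, so a pair counts as 0.75 of a completer. Under a subject-within-sequence model each pair adds one residual degree of freedom. A least-squares design matrix with subject, period and treatment gives the same effective numbers.

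**Step 3: which drop-outs have a pair.** Take 60 − 48 = 12 drop-outs, 4 per sequence. After Period 1 nobody has a pair. After Period 2 the TRR and RTR subjects have one, and the RRT subjects have only R-R.

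| Assumed timing of the 12 | T-R pairs, k | Effective completers, 48 + 0.75k | df, 93 + k | AUC0-t power |
|---|---|---|---|---|
| All after Period 1 | 0 | 48 | 93 | 80.5% |
| 6 after Period 1, 6 after Period 2 | 4 | 51 | 97 | 82.8% |
| All after Period 2 | 8 | 54 | 101 | 84.8% |
| Ceiling: every drop-out misses only one Reference | 12 | 57 | 105 | 86.6% |

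The ceiling needs RRT subjects to miss one Reference and still receive Test, which is unlikely where an event leads to withdrawal.

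**Step 4: Cmax.** Simulation with the 0.760 constant, the cap at CV 50% and the point-estimate limit gives about 95 to 96% with 48 completers at CV 45 to 55%, and about 97 to 98% at the ceiling. Cmax is not the constraint.

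**Step 5: the number in the SAP.** The concentration tables in SAP 15.5 carry n = 59 for Test and for the Reference tables, for both analytes. With 59 completers AUC0-t power is 87.7%. If the 60th subject supplied a pair (effective 59 + 0.75 = 59.75) it would be 88.0%. The unrounded difference is about 0.4 points.

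**The case against.** The strongest reply is that the rule is the basis of the sample size. Protocol 5.2 defines the 48 evaluable subjects as having all assessments, and 8.1 randomises 60 so that 48 such subjects remain. This stands: nothing promised is lost.

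The gain also depends on timing. A subject withdrawn for an event in Period 1 or 2 usually has no usable pair, and the gain can be zero. This stands.

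The rule has some purpose. It gives one common set for AUC0-t, Cmax and sWR, and it fits Protocol 6.9, which counts a subject as compliant only after all periods. A reader might infer that the rule costs power for nothing; the documents do not support that. Equally, sWR does not require the exclusion, since T-R pairs can enter the ratio while R-R pairs enter sWR.

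The printed code could not use the pairs as claimed. With SUBJ nested in TRT, each observation of a pair has its own subject-by-treatment parameter, so the pair adds no residual degrees of freedom. This stands, and the gains above hold only under the SAP 8.1 model.

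A reader might also infer that Protocol 8.6 forbids Table 8 outright. One can answer that Table 8 decides who enters and 8.6 governs removal afterwards. The texts are unaligned rather than flatly contradictory.

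Finally, selection on completion might suggest bias. None is shown, and a pair-based set also conditions on events after dosing, though less.

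**Conclusion.** Table 8 discards valid Test-Reference pairs and, for RRT subjects, valid R-R pairs, although the SAP 8.1 model and the R-R data requirement for sWR do not need this. At the planned 20% drop-out the cost is 0 to 4.3 points of AUC0-t power under the three timing patterns (80.5% to 84.8%), and 6.1 points at the ceiling (86.6%). At 59 completers it is about 0.4 points.

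The tempting reading that the trial falls short of 80% power is not supported, because the 80% was computed on completers.

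The figures rest on assumed drop-out timing, losses spread equally over sequences, equal within-subject variance for Test and Reference as in Protocol 8.1, and subject within sequence in the model. This is a cheap improvement in precision and clarity, not a flaw that threatens the conclusion.

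**What to change.** 1. For the Test/Reference comparison, define the PK set as subjects with evaluable AUC0-t and Cmax in at least one Test and one Reference period and no relevant violation in those periods.
2. Estimate sWR from all subjects with both Reference periods.
3. Report three-period completers as a sensitivity analysis.
4. Use the subject-within-sequence model of SAP 8.1 in place of the printed SUBJ(TRT) term.
5. Align Table 8, Protocol 8.6 and SAP 10.1, and repair the garbled sentence in SAP 10.1. The listed exclusions in 8.6 can otherwise stay.

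The cost is a few lines of text and code, with no new data. The downside is slightly unbalanced data and different counts for the two estimates. If all 12 left after Period 2, for example, the ratio would use 48 + 8 = 56 subjects and sWR 48 + 4 = 52.

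If the primary set is already fixed, as the results wording in SAP 15.2 suggests, keep it and report the all-available-pairs analysis as sensitivity.

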8.4 Description of Statistical Analyses

8.4.1 General Considerations

Statistical analysis will be performed using the computer program package SAS[®] System PPD [REDACTED]. If not stated otherwise, the level of statistical significance will be $\alpha=0.05$. PK data evaluation will be performed based on standard non-compartmental methods using the validated software tool PPD [REDACTED]. Details on the statistical analysis and PK data analysis will be presented in the statistical analysis plan prior to database lock.

The statistical analysis will not be started until all data have been corrected and checked for plausibility, and until all necessary coding and assessments have been completed.

Medical history and AE terms will be coded with Medical Dictionary for Regulatory Activities (MedDRA), version 18.0 or later; concomitant medication will be coded with WHO (World Health Organization) Drug Dictionary, WHO Drug Reference List and Anatomical Therapeutic Chemical Classification System, latest version. Medical History will be coded according to MedDRA, latest version. Versions of dictionaries used for coding will be defined in the Data Management Plan (DMP).

All data recorded during the trial will be presented in individual data listings.

All data will be evaluated as observed, no imputation method for missing values will be used except for missing dates/times in AE data which will be performed for the classification of treatment-emergence, assigning AEs to treatment periods and for calculation of duration. The handling of concentration values below the limit of quantification (BLQ) will be described in the statistical analysis plan.

Summary statistics will be provided for all endpoints.

